3.2 Hypothesis to be Tested

With respect to the primary endpoint Moderate to Severe CIPN at 9 months after first dose of IMP the statistical hypothesis to test is:

$$H_0: \mu_{5\mu\text{mol/kg}} = \mu_{\text{placebo}}$$

$$H_1: \mu_{5\mu\text{mol/kg}} \neq \mu_{\text{placebo}}$$

where μ_x represents the oxaliplatin-dose adjusted Moderate to Severe CIPN event rate at 9 months on treatment x . The treatment effect will be captured as the ratio of event rates, $\Psi = \mu_{5\mu\text{mol/kg}} / \mu_{\text{placebo}}$, so that the preceding null and alternative hypotheses can be reframed as

$$H_0: \Psi = 1 \text{ versus } H_1: \Psi \neq 1$$

A rate ratio <1 favours the PledOx 5µmol/kg group over placebo.

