5.2 Handling of Missing Data in the Primary Endpoint

For the primary endpoint Moderate to Severe CIPN (yes/no) the following methods of imputation will be used for the primary analysis in case of missing:

1. Observed cases (no imputation)
2. “Non-responder” if missing (ie 3 or 4 on FACT/GOG)
3. Tipping point analysis – combinations of missing data values that would change the conclusion. References eg Yan (2009), Rubin (2012)

A tipping point analysis assesses the potential impact of informative missingness by progressively penalizing patients with missing data in the experimental arm. The goal is to find the level of penalization that results in loss of statistical significance on the primary endpoint.

The steps to perform the tipping point analysis are as follows:

1. The NB model as described in Section 5.1.1 is applied to each randomised treatment arm separately based on the observed data in that arm. This will give two parameters for each of the experimental and control groups, the event rate, μ , and the dispersion rate, κ .
2. For each subject, i , in the experimental arm who had $t_i < 9$ months follow-up and who did not record a primary endpoint event in the period $(0 - t_i]$, simulate their event rate, μ_i , by randomly sampling an observation from a $Gamma(shape = 1/\kappa, scale = 1/(\kappa\mu))$ distribution.
3. Using μ_i , the time to event for subject i in the period $(t_i, 9]$ is given by $\Delta_i = -\ln(1 - \omega_i)/\mu_i$ where ω_i is a random deviate from a $U(0,1)$ distribution.
4. If $t_i + \Delta_i \leq 9$ then subject i is considered to have had an event at with an exposure time of $t_i + \Delta_i$. If $t_i + \Delta_i > 9$ then subject i is considered not to have event at with an exposure time of 9 months.
5. Steps 2-4 will result in a full dataset with no missing primary endpoint data over the period (0-9] months.

6. This full dataset is then analysed in the same manner as described for the primary endpoint using the Cochran-Mantel-Haenszel approach and the treatment effect and associated SE are estimated.
7. Steps 2-6 are repeated multiple times and the resulting treatment effect estimates and SEs are combined in SAS via PROC MIANALYZE using Rubin's rules. This will provide the estimated treatment effect having imputed missing data under a missing at random assumption.

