8. Return to Step 2 and now, for each subject, i , in the experimental arm who had $t_i < 9$ months follow-up and who did not record a primary endpoint event in the period $(0 - t_i]$, resimulate their event rate, μ_i , by randomly sampling an observation from a *Gamma*($shape = 1/\kappa, scale = 1/(\kappa(\mu + \varepsilon))$) distribution where ε is some small, positive number. Imputation of control treated patients is unchanged.
9. Repeat Steps 2-7. This will provide the estimated treatment effect having imputed missing data under a missing not at random with the event rate on experimental penalised by the amount ε .
10. Repeat steps 2-9 for penalising the experimental event rate by $\varepsilon, 2\varepsilon, 3\varepsilon, \dots$ until statistical significance is lost.

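### The tipping-point imputations reuse one fixed estimate of the event rate and dispersion, so Rubin's rules leave out the uncertainty in those estimates; the effect is small

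*SAP*

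**What the plan says.** SAP Section 5.2 lists three approaches to missing values of the primary endpoint; the third is a tipping-point analysis in ten steps.

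- **Step 1:** the negative binomial model "is applied to each randomised treatment arm separately based on the observed data in that arm". Each arm thus yields one estimate of the rate μ and one of the dispersion κ.
- **Step 2:** each affected patient's own rate is simulated "by randomly sampling an observation from a" Gamma distribution with those values of μ and κ.
- **Steps 3 to 6:** the rest of the 9 months is simulated for that patient, and the completed data set is analysed by the CMH method of Section 5.1.1.
- **Step 7:** "Steps 2-6 are repeated multiple times and the resulting treatment effect estimates and SEs are combined in SAS via PROC MIANALYZE using Rubin's rules".
- **Steps 8 and 9:** the penalised run returns to step 2 with μ + ε in place of μ. "Repeat Steps 2-7. This will provide the estimated treatment effect having imputed missing data under a missing not at random" mechanism.
- **Step 10:** "Repeat steps 2-9 for penalising the experimental event rate by" successive multiples of ε, until significance is lost.

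No step draws μ and κ from a distribution, bootstraps them or refits them between imputations.

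**The concern.** Rubin's total variance, W + (1 + 1/M)B, assumes that each of the M imputations reflects two sources of uncertainty: the randomness of the missing outcomes given the imputation model, and the error in the fitted model itself. Here only the first varies. The Gamma draw in step 2 does not supply the second, because it describes differences between patients at given μ and κ. More imputations do not help, since the missing component never enters B.

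The quantity reported is the penalty at which the pooled result stops being significant. If B is short, that penalty is larger than proper imputation would give, and the shortfall grows with the share of missing data.

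**Working it through.** **1. The plan's own complete-data standard error.** Section 5.1.1 gives example data of 32/118 events on PledOx 5 µmol/kg and 48/118 on placebo, with a CMH ratio of 0.6869, CI 0.4391 to 1.0745 and p = 0.0999. In single-stratum form its variance is 1/E1 + 1/E2 = 1/32 + 1/48 = 0.0521, so SE = 0.2282. Then 0.6869 × exp(±1.96 × 0.2282) = 0.4392 to 1.0744, and p = 0.0998. The example is reproduced, so this is the within-imputation variance W that enters step 7.

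**2. Closed form, no credit for partial follow-up.** Take an arm of n patients with missing fraction f, m = fn and event probability p.

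- Event-draw variance (kept): m p(1−p).
- Parameter variance (omitted): m² p(1−p)/(n−m).
- Share of B kept: (n−m)/n = 1 − f.

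Dividing by E² and adding both arms gives B = f·Wb as written and B = f/(1−f)·Wb when proper. Wb is the binomial variance (1−p1)/E1 + (1−p2)/E2 = 0.7288/32 + 0.5932/48 = 0.0351.

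| f | SE ratio, as written / proper, W = 0.0521 (SAP) | SE ratio, W = 0.0351 (binomial) |
|---|---|---|
| 10% | 0.997 | 0.995 |
| 20% | 0.985 | 0.980 |
| 30% | 0.966 | 0.954 |
| 40% | 0.936 | 0.917 |

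These are an upper range. Steps 2 to 4 impute only patients who are event-free when lost, and only over the time left to month 9.

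**3. Simulation that follows steps 2 to 7.** Assumptions not in the SAP: loss at month 3 of 9, 118 to 245 patients per arm, rates of 20–27% versus 40–41%, μ taken per month, and a Gamma with mean μ. The proper version redraws μ for each imputation; κ was not redrawn. Step 2 names only the experimental arm while step 8 speaks of imputing controls, so both readings were run.

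| Missing | Increase in B when μ is redrawn | As-written SE short by |
|---|---|---|
| 10% | 8% | 0.1–0.2% |
| 20% | 17–19% | 0.5–0.9% |
| 30% | 28–31% | 1.2–2.2% |

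One case in full, ignoring 1/M: 245 per arm, 27% versus 41%, 30% missing in both arms. As written, SE = 0.1803 and B = 0.00497, so W = 0.1803² − 0.00497 = 0.02754. With the proper B of 0.00645, SE = √(0.02754 + 0.00645) = 0.1844. The p-value moves from 0.018 to 0.021.

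**4. Tipping penalty (events per month), as written → proper, κ = 0.**

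| Scenario | 10% missing | 20% missing | 30% missing |
|---|---|---|---|
| 118 per arm, 20% vs 40% | 0.119 → 0.119 | 0.040 → 0.039 | 0.023 → 0.021 |
| 200 per arm, 25% vs 41% | 0.100 → 0.101 | 0.037 → 0.036 | 0.020 → 0.018 |
| 245 per arm, 27% vs 41% | 0.075 → 0.075 | 0.027 → 0.027 | 0.014 → 0.013 |

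At 30% missing, including the runs with κ = 0.5, the fall is 0.001–0.002, or about 5% (0.020 → 0.019) to 13% (0.015 → 0.013). Penalties were found to three decimals, so these percentages are coarse. At 10% the differences are within simulation noise.

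**5. Is the pooled SE too small in absolute terms?** Using step 2's formulas, the as-written SE is √(0.0521 + f × 0.0351) and the true sampling SE is √(0.0351/(1−f)). At f = 10, 20, 30 and 40% this gives 0.236, 0.243, 0.250 and 0.257 against 0.198, 0.210, 0.224 and 0.242. The as-written SE is too large by 19, 16, 12 and 6%. Repeated-trial simulation agrees: at 245 per arm, 27% versus 41% and 30% missing, the mean SE is 0.171 and the true SD 0.146. With no treatment effect (40% in both arms) the two-sided 5% test rejected in 1.0% of trials at 10% missing and 1.6% at 30%.

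**The case against.** A reader might infer that the pooled standard error is simply too small and that the tipping-point test is therefore anti-conservative. The documents do not support that. The Section 5.1.1 variance treats a yes/no outcome as a Poisson count, and check 5 shows that this excess outweighs the omitted component over the whole range examined. What stands is the comparison with proper imputation under the same CMH analysis. Two errors in opposite directions do not make a justified method, and if the within-imputation variance were corrected the shortfall would be proportionally larger (2.0% against 1.5% at 20% missing in the closed form).

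The effect can fairly be called small. It is negligible up to about 10% missing, and the other two approaches, observed cases and counting missing as non-responder, do not use this loop. The SAP's own example cannot show a tipping point at all: at p = 0.0999 there is no significance to lose. All of this stands and sets the severity.

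The direction also depends on how the Gamma is read. With shape 1/κ, the printed 1/(κμ) gives mean μ only as a rate. Read literally as a scale, the mean is 1/(κ²μ), and a larger ε would lower the imputed rate. That is a separate error; the results here assume the intended form.

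Finally, Section 3.2 says "The treatment effect will be captured as the ratio of event rates", from which a reader might infer that step 7 pools the ratio with a log-scale SE. Section 5.1.1, however, defines SE for log(R_MH) and sets Z = log(R_MH)/SE, and step 6 follows that analysis. Pooling on the log scale is the natural reading; stating it would only add clarity.

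**Conclusion.** The point holds as a minor one. Steps 1 to 10 of Section 5.2 are improper multiple imputation: μ and κ are estimated once and held fixed while steps 2–6, 2–7 or 2–9 repeat, so the variance pooled by Rubin's rules omits the error in those estimates. Relative to proper imputation with the same CMH analysis, the pooled SE is slightly short and the tipping penalty slightly too large.

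The size depends on a missing fraction that the SAP does not give. At 20%, the dropout allowed for in the sample size of Section 2.4, the SE is short by up to about 1% and the penalty moves by 0–0.002 events per month. At 30% the SE is short by about 1–2% and the penalty shifts by about 5–13%. These figures rest on loss at month 3 and on redrawing μ alone; less follow-up before loss would move them towards the closed-form range.

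**What to change.** Put the parameter draw inside the loop. Before step 2 of every repetition, including the penalised runs of steps 8 to 10, draw (μ, κ) for each imputed arm from their estimated sampling distribution, or refit step 1 on a bootstrap sample of that arm. The bootstrap is the simpler route if κ is estimated at or near zero. Add ε to the redrawn μ. For clarity, state in step 7 that log(R_MH) and its SE are pooled and tested against 0, then back-transformed.

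The cost is a sentence or two in the SAP and a few lines of code, and the pooled interval becomes slightly wider. The change belongs in the SAP before the blind is broken, which Section 1 already sets as the point of finalisation.

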2.4 Sample Size

As stated in Introduction the dosing of IMP stopped earlier than planned. Hence, the sample size assumptions originally stated in the protocols do not longer hold. In POLAR-A a total of n=301 patients have been randomised as compared to the planned n=280, and in POLAR-M n=290 patients have been randomised as compared to the planned n=420. The sample size protocol text below are stated for reference.

Protocol text (Section 10.2 in the CSPs)

The assumption of the proportion of patients who will satisfy the criteria for the primary endpoint in the untreated (placebo) study population is based on the results in the SCOT trial. Results were presented at ASCO 2017 and roughly 40% of the placebo population had symptoms graded “quite a bit/very much”, which corresponds to 3 or more in this study.

With 112 patients per group, the **POLAR-A** study has 91% power to detect a reduction (improvement) from 40% to 20% (OR = 0.375) in the primary endpoint using two-sided test controlled at the 0.05 type-I error rate. To account for 20% dropout in the study, in total 280 patients (140 patients per arm) will be randomised.

With 112 patients per group, the **POLAR-M** study has 91% power to detect a reduction (improvement) from 40% to 20% (odds ratio = 0.375) in the primary endpoint using two-sided test controlled at the 0.05 type-I error rate. To account for 20% dropout in the study, in total 420 patients (140 patients per arm) will be randomised.

Sample size assumptions will be monitored in a blinded fashion as part of the regular monitoring of the study. In case there are indications these are not met; a re-estimation of the sample size may occur.

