5.1 Primary Endpoint

5.1.1 Moderate to Severe CIPN

The primary endpoint is defined as the proportion of patients (with moderate or severe chronic CIPN) scoring 3 or 4 in at least 1 of the first 4 items of the FACT/GOG-NTX-13 (i.e., FACT/GOG-NTX-4), targeting numbness, tingling or discomfort in hands and/or feet, 9 months after the first dose of IMP (i.e. PledOx or placebo administered on Day 1, Cycle 1 of mFOLFOX6 chemotherapy).

Baseline is defined as the time of administration of the first dose of IMP (Day 1, Cycle 1).

Moderate to Severe CIPN will derived (SAS) as follows:

```
cipn=0;  
IF ntx1_std=. AND ntx2_std=. AND ntx3_std=. AND ntx4_std=. THEN cipn=.;  
ELSE IF ntx1_std IN('3','4') OR ntx2_std IN('3','4') OR  
      ntx3_std IN('3','4') OR ntx4_std IN('3','4') THEN cipn=1;
```

Primary Analysis – Cochran-Mantel-Haenszel. The primary analysis of the primary endpoint Moderate to Severe CIPN (yes/no) at 9 months after first dose of IMP will be analysed by the Cochran-Mantel-Haenszel (CMH) estimate of the common relative risk of Moderate to Severe CIPN. The treatment effect will be assessed by estimating the ratio of the incidence rates of CIPN in PledOx 5µmol/kg versus Placebo along with its 95% confidence interval and corresponding p-value. The CMH estimate will be adjusted for cumulative exposure of oxaliplatin and stratified by study and region. Incidence rates (95% CIs) for each treatment will also be presented.

Notations. The combined analysis includes two studies (POLAR-A and POLAR-M) and two geographical regions (Asia/Non-Asia), and so there are 4 strata, where

- 1 = POLAR-A / Asia
- 2 = POLAR-A / Non-Asia
- 3 = POLAR-M / Asia
- 4 = POLAR-M / Non-Asia

Treatments are denoted by 1 and 2, where 1 = PledOx 5µmol/kg and 2 = Placebo. For treatment j in the i^{th} strata the cumulative exposure of oxaliplatin is T_{ij} and E_{ij} is CIPN events. Let $T_{i\bullet} = T_{i1} + T_{i2}$ and $E_{i\bullet} = E_{i1} + E_{i2}$ denote total cumulative exposure of oxaliplatin and total CIPN events in the i^{th} strata.

CMH point estimate of the common relative risk across strata. Under $H_0: R_1 = R_2 = R$, Breslow and Day [1] provide the stratified Cochran-Mantel-Haenszel estimate of the common relative risk as

$$\hat{R}_{M-H} = \frac{\sum_{i=1}^k \frac{E_{i1}T_{i2}}{T_{i\bullet}}}{\sum_{i=1}^k \frac{E_{i2}T_{i1}}{T_{i\bullet}}}$$

Also, Robins, Breslow and Greenland [2] provide an estimate of the variance of $\log \hat{R}_{M-H}$ as

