Supportive Analysis of the primary endpoint - Negative Binomial Regression. A supportive analysis of the primary endpoint Moderate to Severe CIPN (yes/no) at 9 months after first dose of IMP will be analysed by a negative binomial regression model adjusted for study (POLAR-A / POLAR-M) and region (Asia / non-Asia). An offset variable will also be used to adjust for the oxaliplatin exposure defined as the logarithm of the cumulative dose of oxaliplatin received by each patient. Estimate of the treatment contrast (rate ratio) and its corresponding 95% confidence interval will be based on the anti-log of the model parameter estimate and CI.

SAS Code Example Negative Binomial Regression using PROC GENMOD

```
PROC GENMOD;
  CLASS study region trt;
  MODEL cipn = study region trt/DIST=negbin LINK=log SCALE=deviance OFFSET=log_exp;
  ESTIMATE 'PledOx 5 µmol/kg vs Placebo' trt 1 -1;
  LSMEANS trt / CL EXP;
RUN;
```

If convergence criterion is not met using PROC GENMOD an alternative using PROC NLMIXED will be used.

SAS Code Example Negative Binomial Regression using PROC NLMIXED

```
PROC NLMIXED;
  PARMs b0 -2 b1 .1 b2 -.01 b3 .1 phi .1;
  eta = log_exp + b0 + b1*(study=1) + b2*(region=1) + b3*(trt=0);
  mu = exp(eta);
  LL = y*log(phi*mu) - (y+(1/phi))*log(1+(phi*mu)) + lgamma(y+(1/phi)) -
lgamma(1/phi) - lgamma(y+1);
  MODEL y ~ general(LL);
RUN;
```

Exploratory Analysis – Exact Logistic Regression. An exploratory analysis of the primary endpoint Moderate to Severe CIPN at 9 months after first dose of IMP will be analysed by exact logistic regression model adjusted for study (POLAR-A / POLAR-M) and region (Asia / non-Asia). Estimate of the treatment effect and its corresponding 95% confidence interval will be based on the odds-ratio.

SAS Code Example Exact Logistic Regression

```
PROC LOGISTIC DESC;
  CLASS study region trt(ref='0: Placebo');
  MODEL cipn = study region trt;
  EXACT trt;
RUN;
```

Using the same example data presented above, a crude estimate of the odds-ratio then is:

$$(0.27/0.73) / (0.41/0.59) = 0.53$$

Table 4 Example data: Exact Logistic Regression of Moderate to severe CIPN 9 months after first dose of IMP

	N	CIPN (%)	Odds-ratio	95% CI	P-value
PledOx 5 µmol/kg	118	27.1	-	-	-
Placebo	118	40.7	-	-	-
PledOx 5 µmol/kg vs Placebo	236	-	0.54	[0.31;0.94]	0.0293

Data Presentations

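### The starting point of the tipping-point analysis imputes from one rate per arm although the analysis it feeds is stratified by study and region, so its missing-at-random label needs a stronger assumption than it states (minor)

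*SAP*

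**What the plan says.** SAP Section 5.2 lists three approaches to a missing primary endpoint: observed cases, missing counted as an event, and a tipping-point analysis. The steps of the third that matter here are these.

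- Step 1: "The NB model as described in Section 5.1.1 is applied to each randomised treatment arm separately based on the observed data in that arm". The result is described as two numbers per arm, an event rate μ and a dispersion κ.
- Step 2: each experimental-arm patient with follow-up t_i under 9 months and no event so far gets a rate drawn from a Gamma distribution that contains only μ and κ.
- Steps 3 and 4: that rate decides whether an event falls between t_i and 9 months.
- Step 6: the completed data go to the primary analysis.
- Step 7: the pooled result is labelled: "This will provide the estimated treatment effect having imputed missing data under a missing at random assumption".
- Steps 8 to 10: the penalty ε is added to μ and increased until significance is lost.

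The model cited in step 1 is, in Section 5.1.1, "analysed by a negative binomial regression model adjusted for study (POLAR-A / POLAR-M) and region (Asia / non-Asia"), with log cumulative oxaliplatin dose as offset. Of the primary analysis that receives the data, Section 5.1.1 says: "The CMH estimate will be adjusted for cumulative exposure of oxaliplatin and stratified by study and region". That makes four strata.

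**The concern.** A model with study and region terms has no single event rate per arm, so the output described in step 1 does not match the model it cites. Read as written, the imputation is coarser than the analysis that follows. An adjuvant patient in Asia and a metastatic patient elsewhere receive draws from the same distribution and are then placed in different strata.

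Imputing from arm alone is sound if, given arm, missingness has nothing to do with study or region. Missing at random given the analysis strata would allow missingness to differ between them. If both the event rate and the missing fraction differ by stratum, patients are imputed at a rate that belongs partly to another stratum, and the combined ratio moves before any penalty is applied. Every value of ε at which significance is lost is counted from that start.

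**Working it through.** **The plan's own figure.** The SAP gives no numerical result for the tipping-point analysis. Its design power does reproduce. With 112 per group, 40% versus 20% and two-sided 0.05: (0.20 − 1.96·√(2·0.30·0.70/112)) / √((0.24 + 0.16)/112) = (0.20 − 0.1200)/0.0598 = 1.338, which gives 0.910 against the stated 91%. It has no bearing on this point.

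**Inputs.** Month-9 missingness by study, event rates by study and κ are not given, so all of these are assumptions. Oxaliplatin dose per patient is taken as equal and arms as equal in size, so the Mantel-Haenszel ratio becomes Σ n_i·p_i1 / Σ n_i·p_i2. Two study strata are used. The Gamma is taken to have mean μ per month; whether the scale and time unit are printed correctly is a separate matter.

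**Formulas.** For risk p_i and missing fraction m_i in stratum i:

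- Arm-wide rate: r = Σ n_i(1 − m_i)p_i / Σ n_i(1 − m_i).
- With constant hazards and κ near 0, a patient lost at month t ends with risk q_i = 1 − (1 − p_i)^(t/9)·(1 − r)^((9 − t)/9).
- Stratum risk after imputation: p_i(1 − m_i) + m_i·q_i.

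**Main scenarios.** There are 130 (POLAR-A) and 65 (POLAR-M) patients per arm, placebo risks are 40% and 25%, and both arms are imputed.

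- A: true ratio 0.60 in both studies. Missing 10%/45% on PledOx and 10%/30% on placebo.
- B: true ratio 0.50 in POLAR-A and 1.00 in POLAR-M. Missing 10%/35% in both arms.
- C: as B, with the two study ratios swapped.

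Scenario A at t = 0:

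- PledOx rate: r = (117·0.24 + 35.75·0.15)/152.75 = 0.219. Placebo rate: r = (117·0.40 + 45.5·0.25)/162.5 = 0.358.
- POLAR-M PledOx: 0.55·0.15 + 0.45·0.219 = 0.181. POLAR-M placebo: 0.70·0.25 + 0.30·0.358 = 0.282. Ratio 0.64.
- POLAR-A: 0.238 and 0.396.
- Combined: (130·0.238 + 65·0.181)/(130·0.396 + 65·0.282) = 0.612.

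At t = 6 the missing POLAR-M PledOx patient has q = 1 − 0.85^(6/9)·0.781^(3/9) = 0.174 instead of 0.219, and the combined ratio is 0.604.

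| Scenario | True combined ratio | t = 0 | t = 3 months | t = 6 months |
|---|---|---|---|---|
| A | 0.600 | 0.612 | 0.608 | 0.604 |
| B | 0.619 | 0.592 | 0.601 | 0.610 |
| C | 0.881 | 0.908 | 0.901 | 0.892 |

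**More extreme scenarios.** Only the experimental arm is imputed, t = 0, with 150 and 97 per arm and a true ratio of 0.67.

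- Placebo risks 40%/20%, missing 15%/33%: 0.693.
- Placebo risks 40%/20%, missing 5%/40%: r = (142.5·0.268 + 58.2·0.134)/200.7 = 0.229. Imputed PledOx events are 56.6 against 79.4 on placebo, a ratio of 0.713. Treating imputed counts as observed, SE = √(1/56.6 + 1/79.4) = 0.174 and z = −1.95. With study-specific rates the ratio is 0.670 and z = −2.26.
- Placebo risks 20%/40%: 0.644 with missing 15%/33% and 0.621 with missing 5%/40%.
- Equal missing fractions (20%/20%), or equal rates in both studies: 0.670, unchanged.

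**Event-free follow-up in the draw.** Under the SAP's Poisson-gamma model, a patient event-free to t has a rate distributed as Gamma with shape 1/κ and inverse scale 1/(κμ) + t. At a 9-month risk of 27% and t = 6, conditioning changes the remaining risk as follows.

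- κ = 1 (μ = 0.0411): unconditional 1 − 1/(1 + 3μ) = 0.110; conditional 1 − (1 + 6μ)/(1 + 9μ) = 0.090.
- κ = 0.5: 0.105 to 0.095.
- κ = 0.01: 0.0997 to 0.0995.

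For the PledOx arm of example Table 2 (32 events in 118 patients), the negative binomial log-likelihood is −73.76 at κ = 0.0001, −75.84 at 0.5 and −77.75 at 1. Data of 0s and 1s push κ towards zero, where this part almost vanishes.

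**The case against.** Several parts of the opposing case stand.

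- A reader might infer that the scheme is not missing at random at all. The text does not support that. Imputation that is ignorable given arm is a legitimate missing-at-random assumption; its conditioning set is just narrower than the analysis strata.
- A reader might infer that follow-up and earlier scores are ignored. They are not. Step 2 covers only experimental-arm patients with no event so far, so earlier scores decide who is imputed, and t_i sets where the remaining interval starts. Both are absent only from the rate draw.
- Step 1 does cite a covariate-adjusted model, so a programmer might well use stratum-specific rates. The description of two parameters per arm points the other way. The text needs correcting on either reading.
- A reader might infer a bias in favour of PledOx. Scenario B moves that way, but A and C move against it.
- Table 1 might be read as showing unequal month-9 missingness. It counts cycles of IMP among dosed patients: at least 6 cycles in 257/297 (87%) in POLAR-A and 194/285 (68%) in POLAR-M. The dosing hold cut these short, and the POLAR-M count includes the 2 µmol/kg arm. It makes unequal completeness plausible and does not measure it.

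What the opposing case does not remove is the mismatch itself: one rate per arm feeds an analysis in four strata, under a label that does not say what is conditioned on.

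**Conclusion.** The point holds as a minor one. As written, the zero-penalty result is valid only if missingness is unrelated to study and region given arm, which is stronger than missing at random given the strata of the analysis.

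The shift in the starting ratio needs both event rates and missing fractions to differ between strata. It was 0.004 to 0.027 in the main scenarios, smaller the longer patients are followed before dropout, and up to 0.05 in more extreme ones with no follow-up before dropout. It can go either way. All missing fractions and study-specific rates behind these sizes are assumed.

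The z of −1.95 in one extreme case should not be read as a forecast that significance will be lost. It takes 5% against 40% missing, a twofold difference in risk between studies and no follow-up before dropout, and it leaves out between-imputation variance. The result affects one of three missing-data approaches.

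**What to change.** - **Steps 1, 2 and 8:** use the fitted rate for the patient's own study and region, from the model already cited, and add the penalty ε to that rate.
- **Step 2:** for consistency, draw from the Gamma conditional on no event by t_i (shape 1/κ, inverse scale 1/(κμ) + t_i). The effect is negligible when κ is near 0.
- **Step 7:** state that the assumption is missing at random given arm, study and region.

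The cost is a few lines of code and slightly less precise rates in the smaller strata. A logistic imputation model that also uses the last NTX-4 score is an option and is not needed to settle this point.
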